4. AMENDMENTS AND UPDATES

Amendment number	Date	Substantial or administrative amendment	Protocol section(s) changed	Summary of amendment(s)	Reason
1.0	16 April 2019	Administrative		
1. Added references to guidelines on Protection of Human Subjects and AE reporting.2. Update to text in the MANAGEMENT AND REPORTING OF ADVERSE EVENTS/ADVERSE REACTIONS section to align with Pfizer SOPs.	Alignment with the Global IRIS protocol.
2.0	13 August 2020	Substantial	4, 5, 6, 7, 8, 9, 10, 11, 12	
1. Addition of Colombia.	To expand the scope of data collection and include a wider geographic region within Latin America.

5. MILESTONES

Milestone	Planned date	Actual date completed
Start of data collection (Costa Rica and Panama, Chile, Peru, Mexico and Argentina)	Q1/Q2 2019	01 June 2019
End of data collection	Q2/Q3 2019	30 September 2019
Study Report – All Countries (Costa Rica and Panama, Chile, Peru, Mexico and Argentina)	Q3 2019	01 November 2019
Start of Colombia data collection	August 2020	
End of Colombia data collection	October 2020	
Final study report – all markets	December 2020	

6. RATIONALE AND BACKGROUND

Breast cancer is the most common diagnosed cancer and the most common cause of cancer-related death in females worldwide; Latin America is no exception. There were 1.67 million new cases of breast cancer diagnosed globally in 2012, which equated to 12% of all diagnosed cancers.¹ Out of these new cases 522,000 women died of the disease, which represented 15% of female deaths from cancer in 2012.¹ In Latin America, an estimated 114,900 women are diagnosed with breast cancer every year and 37,000 die of the disease in the region.¹

There is a huge worldwide variation in breast cancer survival rates, ranging from 80% or more in North America, Sweden and Japan to 60% in middle-income countries and as low as 40% in low-income countries.² Even though mortality rates from breast cancer have been in decline during recent years, the mortality rate is higher in Argentina (17.56 per 100 000 women in 2012) than in most other Latin American countries, as well as some other European and North American countries.^{1,3,4}

The 5-year survival rate for women with stage 0/I breast cancer is near to 100%, compared to that of stage II and III, which are 93% and 72% respectively. Women who are diagnosed with metastatic or stage IV breast cancer have a much lower 5-year survival rate of 22%.⁵

An increased understanding of breast cancer has enabled enhanced profiling of different disease subtypes. Subtype classification is essential in order to decide on the appropriate treatment regime. Breast tumors are grouped according to the expression of hormone receptors (HR) and human epidermal growth factor receptor 2 (HER2). Overall HR status is the most important biomarker for breast cancer classification. Tumors that are HR+ grow in response to increased levels of the hormones estrogen and progesterone. HR+ breast tumors are the most favorable, as they respond well to hormone therapies. In contrast HR- breast tumors do not respond well to hormone therapies. These tumors are known to be the most aggressive cancers, in regards to tumor size, grade, stage and patient outcome. HER2 positive (HER2+) breast tumors represent around 15% of all breast tumors. These tumors tend to be more aggressive and faster growing than HER2 negative (HER2-) tumors. HR+/HER2- breast cancer is the most common breast cancer subtype in Argentina, affecting 70% of patients.⁶ Around 15-20% of breast tumors do not contain HR or HER2; these are known as triple negative breast cancers.⁷

Over the past few decades, hormonal therapies such as letrozole and fulvestrant have emerged as the preferred treatment for HR+ breast cancers. Following the success of the phase II PALOMA-1 trial, the FDA granted accelerated approval of the CDK4/CDK6 inhibitor palbociclib that causes cell cycle arrest to be used in combination with letrozole to treat advanced/metastatic HR+/HER2- post-menopausal breast cancer. The PALOMA-1 trial demonstrated median progression-free survival of 20.2 months for post-menopausal patients with advanced/metastatic HR+/HER- breast cancer receiving letrozole in combination with palbociclib vs. 10.2 months in patients receiving letrozole and placebo.⁸ The follow up phase III PALOMA-2 trial demonstrated median progression free survival of 24.8 months for post-menopausal patients with advanced/metastatic HR+/HER- breast cancer receiving

letrozole in combination with palbociclib vs. 14.5 months in patients receiving letrozole and placebo.⁹ The label has since been expanded to include any aromatase inhibitor in this indication.¹⁰

In October 2016, palbociclib was granted approval to be used in combination with fulvestrant. This was following the success of the phase III PALOMA-3 trial, conducted in patients with advanced/metastatic HR+/HER- breast cancer that had relapsed or progressed during endocrine therapy. The PALOMA-3 trial demonstrated a median progression-free survival of 10.8 months in those receiving fulvestrant in combination with palbociclib vs. 4.8 months in patients receiving fulvestrant with placebo.¹⁰

The Global IRIS (Ibrance Real World Insights) study was the first multi-country retrospective chart review of women treated with palbociclib-based regimens according to approved indications in real-world clinical practice, aiming to describe their demographic and clinical characteristics, treatment patterns, and to assess clinical outcomes.¹¹ The Global IRIS study has already been conducted in North American and European markets, and was completed in February 2020, and a first wave of Latin American data was completed in September 2019. Previously data were also collected in Argentina as part of the IRIS Global study, for palbociclib + aromatase inhibitor and palbociclib + fulvestrant received as per the labelled indication across all lines of therapy, not solely restricted to first line treatment.¹²⁻¹⁵ There remains a need to understand the wider use of palbociclib across further Latin American markets, in addition to understanding the complete picture of first line use, regardless of label.

There is currently scarce information, and limited follow up data, regarding palbociclib use in routine clinical practice at the first line, and associated outcomes, as a result of the recent approval of palbociclib in Latin America. Therefore, real world data on the characteristics, treatment patterns and clinical outcomes among patients receiving palbociclib combinations to treat HR+/HER- ABC/ MBC at first line, regardless of combination partner or labelled use, will provide valuable insight to help inform treatment decisions.

7. RESEARCH QUESTION AND OBJECTIVES

The primary objective of this real-world study is to describe patient demographics, clinical characteristics, treatment patterns and clinical outcomes of adult female patients who have received palbociclib combination treatments as first line therapy, regardless of combination partner and labelled use:

Argentina:

- Palbociclib in combination with letrozole as early endocrine therapy to treat advanced/metastatic HR+/HER2- post-menopausal breast cancer (ARG:14th December 2015);

- Palbociclib in combination with fulvestrant for the treatment of women with HR+/HER2- ABC/MBC with disease progression following endocrine therapy (ARG: 16th August 2016).

Chile:

- Palbociclib in combination with letrozole as initial endocrine-based therapy for the treatment of postmenopausal women with HR+/HER2- locally ABC/MBC (June 2015);
- Palbociclib in combination with fulvestrant for the treatment of woman with HR+/HER2- ABC/MBC with disease progression following endocrine therapy (June 2015).

Colombia:

- Palbociclib in combination with letrozole as initial endocrine therapy to treat advanced/metastatic HR+/HER2- ABC/MBC in post-menopausal women (November 2018);
- Palbociclib in combination with fulvestrant for the treatment of women with HR+/HER2- ABC/MBC with disease progression following prior endocrine therapy (November 2018).

Costa Rica:

- Palbociclib in combination with aromatase inhibitor for the treatment of women with HR+/HER2- locally ABC/MBC (August 2016);
- Palbociclib in combination with fulvestrant for the treatment of woman with HR+/HER2- ABC/MBC who have received prior endocrine therapy (August 2016).

Panama:

- Palbociclib in combination with aromatase inhibitor as initial endocrine based therapy in postmenopausal women with HR+/HER2- locally ABC/MBC (July 2017);
- Palbociclib in combination with fulvestrant for the treatment of women with HR+/HER2- ABC/MBC with disease progression following endocrine therapy (July 2017).

Perú:

- Palbociclib in combination with aromatase inhibitor as initial treatment with endocrine basis for post-menopausal women with HR+/HER2- locally ABC/MBC (May 2016);

- Palbociclib in combination with fulvestrant for the treatment of woman with HR+/HER2- ABC/MBC with disease progression following endocrine therapy (May 2016).

Mexico:

- Palbociclib in combination with letrozole as initial endocrine therapy in postmenopausal women with HR+/HER2- locally ABC/MBC (June 2016);
- Palbociclib in combination with fulvestrant for the treatment of woman with HR+/HER2- ABC/MBC who have received prior treatment (June 2016).

7.1. Primary Objectives

- To describe the demographic and clinical characteristics of patients who have received palbociclib combination treatments as first line treatment, regardless of combination partner and labelled use.
- To summarize adjuvant therapies received for the treatment of early or locally advanced breast cancer (Stages 0-IIIa).
- To describe treatments received in the advanced/metastatic setting, before and after palbociclib combination use.
- To describe dosing and dose changes, interruptions, delays, and discontinuations associated with palbociclib use in clinical practice.
- To describe supportive therapies received by patients while receiving palbociclib combination treatments.
- To determine clinical outcomes including (but not limited to).
 - Proportion of patients who are progression free at multiple intervals (eg, 12, 18 months).
 - Objective response rate (ORR) - depending on availability of follow-up data.
 - Proportion of patients alive 1- and 2-year post palbociclib combination initiation - depending on availability of follow-up data.

7.2. Exploratory Objectives

- To evaluate time to progression (TTP)/Progression Free Survival (PFS) associated with palbociclib combination treatments – depending on availability of follow-up data.

8. RESEARCH METHODS

8.1. Study Design

This study will be conducted as a retrospective medical record review of patients who have received palbociclib combination treatments as first line treatment regardless of combination partner and labelled use. Upon completion, the study will comprise of a medical record review conducted in Argentina, Chile, Peru, Mexico, Colombia and a combined sample in Costa Rica and Panama. Data collect for Argentina, Chile, Peru, Mexico, Panama and Costa Rica were completed in September 2019, data collection for Colombia is due in August 2020. The study design is outlined in [Figure 1](#). The study design is similar to the IRIS Global study previously conducted (protocol no. A5481090).^{10,11}

Data collection will be online via electronic data capture using electronic case report form (eCRF). In Colombia eligible physicians will be invited to complete an eCRF for between 6-8 patients that meet the study criteria. Each eCRF will take around 25 minutes to complete. Patient eligibility will be confirmed by treating physicians. In order to allow for a sufficiently long observational window, treating physicians will be asked to go back to a specific point in time, the index date, and sequentially select the medical records of the next 'n' patients who meet the inclusion criteria. The 'index date' will be defined as 60 days after the physician first prescribed palbociclib + partner therapy following the availability of specific indication in the market (eg, If palbociclib + letrozole was available Dec 14, 2015 in Argentina and the physician initiated a patient on palbociclib+ letrozole the next day, the index date will be Feb 12, 2015). The index date will differ for the specific indications/combination partners if approved on different dates. Approval dates can be found in [Section 6](#).

[figure not shown]
The advantage to a retrospective medical record review approach over a database analysis is that of being designed specifically to collect data that fulfils the study objectives. Thus, it readily collects and informs on all key drug related clinical outcome measures of critical importance to this study, in a consistent manner, across countries. The resulting data set enables direct comparisons across markets, delivering in turn greater confidence in the reliability of conclusions drawn from the research. An additional advantage of this approach lies in the ability to obtain information that only the treating physician may be aware of, such as the reasons for treatment switches or discontinuations or more perceptive questions that rely on the physician's professional opinion.

8.1.1. Medical Record Review

Upon study completion the medical record review will capture data from approximately 790-890 patients on demographics, clinical characteristics, disease history, treatment history, palbociclib dosing, clinical outcomes and post-palbociclib combination therapy treatment data (n=647 already achieved, approximately n=200 expected). The study will be descriptive in nature therefore no control or comparator groups will be included.

Data collection in Argentina, Chile, Costa Rica and Panama, Peru and Mexico has already been conducted between July – September 2019. Data collection in Colombia is planned in August 2020.

Figure 1. Study Design Depicting the Proposed Time Frame for the Medical Record Reviews

8.2. Setting

Upon study completion data will be collected from 7 countries. Approximately 30-40 physicians will be recruited in Colombia. Data will be collected retrospectively at a single point in time from patient medical records. To date, 6 physicians in Costa Rica, 1 in Panama, 1 in Chile, 15 in Mexico, 41 in Argentina and 5 in Peru completed eCRFs.

Screening questions/recruitment criteria will ensure the relevant physicians are selected and all other non-qualifying physicians will be excluded. In addition, a representative geographical split and private/public practice split for physicians will be sought where possible to ensure a representative sample.

To be eligible, physicians must have treated or be treating four or more HR+/HER2- ABC/MBC patients who meet the eligibility criteria for the study. This will ensure that recruited physicians will be able to complete the minimum number of eCRFs required to participate in the study. Once physicians have been recruited, they must go back to a specific index date, defined in [Section 7.1](#), and select the next 'n' number of eligible patient records from patients who have been treated with a palbociclib combination. The consecutive approach to recruitment will be stressed to each participating physician to limit selection bias. Physicians will confirm patient eligibility.

Patient records must meet the following criteria to be eligible for the medical record reviews. They must be female, over 18 years of age and they must have been diagnosed with HR+/HER2- ABC/MBC. Patients must have received palbociclib as a first line therapy. For the chart review, palbociclib and letrozole/aromatase inhibitor must have been initiated a minimum of 6 months prior to date of medical chart review, and palbociclib and fulvestrant must have been initiated a minimum of 3 months prior to date of medical chart review. This will permit the capture of meaningful clinical outcomes data.

A full list of the eligibility criteria can be found in [Section 8.2.1](#).

In order to ensure that sufficient data is captured for each indication, indication quotas will be enforced. This will be determined on a country by country basis.

8.2.1. Inclusion Criteria

Physician inclusion criteria:

- Oncologist or gynecologist.
- Responsible for treating $\geq 4-10$ (depending on country) ABC/MBC patients who meet the eligibility criteria.
- Agrees to participate in the study and complete the CRFs within the data collection period.

Patient inclusion criteria:

- ≥ 18 years old.
- HR+/HER2- breast cancer diagnosis with confirmed metastatic or advanced disease.
- Received palbociclib as a first line therapy.
- No prior or current enrolment in an interventional clinical trial for ABC/MBC.
- Minimum of three months of follow up data since palbociclib with fulvestrant initiation, or minimum of six months of follow up data since palbociclib with letrozole/aromatase inhibitor initiation.

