**TREATMENT PATTERNS AND CLINICAL OUTCOMES AMONG PATIENTS IN
LATIN AMERICA RECEIVING FIRST LINE PALBOCICLIB COMBINATIONS
FOR HORMONE RECEPTOR POSITIVE/ HUMAN EPIDERMAL GROWTH
FACTOR RECEPTOR 2 NEGATIVE (HR+/HER2-) ADVANCED/METASTATIC
BREAST CANCER IN REAL WORLD SETTINGS**

This document contains confidential information belonging to Pfizer. Except as otherwise agreed to in writing, by accepting or reviewing this document, you agree to hold this information in confidence and not copy or disclose it to others (except where required by applicable law) or use it for unauthorized purposes. In the event of any actual or suspected breach of this obligation, Pfizer must be promptly notified.

Study Information

Title	Treatment Patterns and Clinical Outcomes Among Patients in Latin America Receiving First Line Palbociclib Combinations For hormone receptor positive/ human epidermal growth factor receptor 2 negative (HR+/HER2-) Advanced/Metastatic Breast Cancer in Real World Settings.
Protocol number	A5481125
Protocol version identifier	Version 3.0
Date	13 August 2020
Date of last version of protocol	16 April 2019
Active substance	L01XE33 - Palbociclib
Medicinal product	Ibrance (palbociclib)
Research question and objectives	To describe patient demographics, clinical characteristics, treatment patterns and clinical outcomes of adult female patients who have received palbociclib combination treatments as first line therapy, regardless of combination partner and labelled use in real world settings across Latin America.
Primary objectives	
To describe demographics and clinical characteristics of patients who have received palbociclib combination treatment as a first line therapy, regardless of combination partner and labelled use.	
To describe adjuvant therapies received for the treatment of early or locally advanced breast cancer (Stages 0-IIIa).	
To describe treatments received in the advanced/metastatic setting, before and after palbociclib combination use.	
To describe dosing and dose changes, interruptions, and delays associated with palbociclib use in clinical practice.	

To detail supportive therapies received by patients while receiving palbociclib combination treatment.

To determine in overall population and defined subgroups, clinical outcomes including.

Proportion of patients who are progression free at specific intervals (eg, 6, 12, 18 months).

Objective response rate (ORR).

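### The clinical-trial criterion in 8.2.1 has no reference date; read at chart review, it also drops women who progressed on first-line palbociclib and then joined a trial

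*Combined protocol and SAP*

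**What the plan says.** The patient inclusion criteria (8.2.1) include "No prior or current enrolment in an interventional clinical trial for ABC/MBC". No date or treatment period is attached. The eligibility summaries in the Abstract and in 8.2 leave this criterion out, so they do not supply one. The follow-up criterion, by contrast, is dated: under 8.2, palbociclib with an aromatase inhibitor "must have been initiated a minimum of 6 months prior to date of medical chart review".

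Three statements govern how the criteria are applied:

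- Section 8.2: "Data will be collected retrospectively at a single point in time from patient medical records".
- Section 8.1: "Patient eligibility will be confirmed by treating physicians".
- Section 8.1: from the index date, physicians "sequentially select the medical records of the next 'n' patients who meet the inclusion criteria".

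Two primary objectives are affected. The first is the progression-free proportion, given in the study information table as "Proportion of patients who are progression free at specific intervals (eg, 6, 12, 18 months") and in 7.1 with 12 and 18 months as the examples. The second, in 7.1, is "To describe treatments received in the advanced/metastatic setting, before and after palbociclib combination use".

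**The concern.** A cohort defined by starting first-line palbociclib should be selected on what was known at that start. Here the physician decides months or years later, with the whole record open. Suppose two women start palbociclib plus letrozole on the same day. One is still progression-free at review and is included. The other progresses at month 9 and joins a second-line trial; at review she has prior or current enrolment and is passed over. The next eligible record takes her place. The plan does not call for a count of such records.

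A later-line trial is usually entered because first-line treatment has failed, so this rule tends to remove progressors. At stake are the progression-free proportions, the exploratory PFS/TTP analysis, and the description of treatment after palbociclib. Section 8.10 says systematic selection will remove patient identification bias and does not mention this exclusion among the limitations.

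**Working it through.** **Reading the criterion.** The plan never says that trial enrolment is judged at review, and never says that it is judged at palbociclib start. Three points favour review time.

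- Eligibility is confirmed when the record is read.
- The minimum follow-up criterion beside it can only be judged then.
- For a woman on first-line treatment, prior enrolment in an ABC/MBC trial would seldom arise before palbociclib start. The word has most of its content at review.

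This is a strong inference, not stated text.

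**Size.** The plan gives no expected progression-free proportion and no later-line trial rate, so there is no figure to reproduce. What follows is an illustration.

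Inputs from the documents:

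- Median PFS 24.8 months (section 6, palbociclib plus letrozole).
- Longest Colombian follow-up of about 21 months: approval November 2018 (section 7), plus 60 days to the index date (8.1), to collection ending October 2020 (section 5).
- Records: 469 + 99 + 8 + 41 + 30 = 647 completed, plus about 200 = 847 (Table 2).

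Assumptions, not from the documents:

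- PFS is exponential.
- Every record is reviewed at the same month F, taken as 18 or 21.
- A share q of women who progressed before F has entered a trial and is passed over, with q = 5%, 10% or 20% and the same for early and late progressors.

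Formulas:

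- S(t) = exp(−ln2 × t / 24.8)
- Observed(t) = [S(F) + (1−q)(S(t) − S(F))] / [S(F) + (1−q)(1 − S(F))]

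This gives S(12) = 0.7151, S(18) = 0.6047 and S(21) = 0.5560.

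- Low end, q = 5%, F = 21: (0.5560 + 0.95 × 0.1591) / (0.5560 + 0.95 × 0.4440) = 0.7071 / 0.9778 = 72.3%, an excess of 0.8 points.
- High end, q = 20%, F = 18: (0.6047 + 0.80 × 0.1104) / (0.6047 + 0.80 × 0.3953) = 0.6930 / 0.9209 = 75.2%, an excess of 3.7 points.

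| q | 12-month, F = 18 | 12-month, F = 21 |
|---|---|---|
| 0 | 71.5% | 71.5% |
| 5% | 72.4% (+0.9) | 72.3% (+0.8) |
| 10% | 73.3% (+1.8) | 73.2% (+1.7) |
| 20% | 75.2% (+3.7) | 75.0% (+3.5) |

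**Sign.** Let early progressors (before month 12) enrol with share a and late ones with share b. The 12-month figure is then N / [N + (1−a)(1 − S(12))], where N = S(F) + (1−b)(S(12) − S(F)). At F = 21 and b = 10%, N = 0.6992.

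- a = 5%: 0.6992 / (0.6992 + 0.95 × 0.2849) = 0.7209, still 0.6 points too high.
- a = 0: 0.6992 / (0.6992 + 0.2849) = 0.7105, about 0.5 points too low.

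With review at month 36, possible only where approval came earlier, 5% early and 10% late leaves the figure unchanged, and 0% early and 10% late lowers it to 70.5%.

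**Scale.** The binomial 95% half-width at 12 months is 1.96 × √(0.7151 × 0.2849 / n): 3.0 points for n = 847 and 6.3 for n = 200.

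**Post-palbociclib treatment.** No model is needed here. If the criterion is applied at review as written, every woman who had trial therapy after palbociclib is excluded, and its recorded frequency is zero whatever the truth.

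**The case against.** The strongest reply is that the plan does not say when enrolment is assessed. Physicians are sent back to an index date, so a reading relative to palbociclib initiation is open. Section 8.10 also says patient selection will be further defined in the CRFs, which are not in the file; they may fix the date, and may already list clinical trial as a later treatment. This stands in part. A reader might infer that the plan sets the assessment at chart review, and it does not. But 8.10 mentions only approval dates as the further detail. If the date is left open, 30-40 Colombian physicians may each decide for themselves, with no source data verification (8.9). The wording needs a date on either reading.

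A second reply is that the direction and size are not established. This also stands. A reader might infer that the progression-free proportions are inflated as a matter of fact. The documents give no trial-entry rate, and the sign depends on who enrols. Upward bias remains the more likely direction, because at any fixed review date early progressors have had longer to enter a trial. The size also depends on follow-up. In Argentina (469 records, letrozole combination approved December 2015, review in mid-2019) follow-up could reach about 41 months, and q = 10% then adds only about 1.0 point at 12 months.

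Third, at q of 5-10% the effect is smaller than the sampling error, and the study is descriptive. That limits its weight, but a selection bias does not shrink as records are added.

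Fourth, 647 of about 847 records are already collected, and a change for Colombia alone makes eligibility differ between countries, although 8.1 relies on consistent collection for cross-market comparison. This is a real cost, and it has to be disclosed.

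**Conclusion.** The concern holds as a missing reference date with a probable consequence. As written, and applied by physicians at a single retrospective review, the criterion makes entry depend on an event after baseline that is linked to progression. The likely effect is an upward bias in the progression-free proportions and PFS/TTP. In the illustration it is about 0.8 to 3.7 points at 12 months, resting on exponential PFS with a 24.8-month median, review at 18 to 21 months, and an assumed 5-20% trial entry that is equal for early and late progressors. The documents support none of these trial-entry shares in particular, and a small downward bias is possible if mainly late progressors enrol. The loss of trial therapy from the post-palbociclib objective needs no assumption about size or sign, only the review-time reading and application of the criterion as written. The point is worth correcting before the Colombian records are read; it does not by itself invalidate the study.

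**What to change.** For Colombia, replace the criterion in 8.2.1 and the screener with: *Not enrolled in an interventional clinical trial for ABC/MBC before or at palbociclib initiation, and palbociclib not given as part of such a trial; later trial enrolment does not exclude.* Make sure the eCRF offers clinical trial as a subsequent-treatment category.

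For the 647 completed records, establish and report how the criterion was applied and, if retrievable, how many records were passed over because of it. If it was applied at review, list it in 8.10 as a probable upward bias, and show Colombian outcomes separately as well as pooled.

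The cost is one sentence and at most one response option, plus a query to those who ran the completed collection. The downside is a difference in eligibility wording between Colombia and the completed countries, which the report must disclose.
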